Materials and methods

Trial design

Single-blind, randomized controlled trial with the aim of evaluating the effect of MT, added to a standard neurorehabilitation protocol, in a selected population of post-acute patients.

Participants

We will consecutively recruite all post-stroke patients admitted to our neurorehabilitation clinic.

Inclusion criteria are as follows:

- Ischemic/hemorrhagic stroke, which determines hemiparesis or hemiplegia.
- Time post onset no longer than 4 weeks
- Age between 18 and 80 years.
- First stroke or stroke recurrence without previous functionally evident motor outcomes.
- MMSE (Mini Mental State Examination) ≥ 24 (29-30)
- Absence of global aphasia. Comprehension deficit, when present, should be minimal, mild or moderate (Token Test score, Aachener Aphasie Test < 40) (33-34)
- Spatial neglect (can be present or not)
- Ideomotor apraxia (can be present or not)
- No other pathologies (e.g., upper limb joint-muscle) that could interfere with motor recovery
- No other seriously invalidating clinical conditions (cardiopathies, bronco pneumopathies)

The recruitment will take place according to the following specifications: during the daily clinical briefing of each Operative Unit of our Centre, physicians inform the physiotherapist coordinators about the patients admitted for post-stroke hemiparesis and coordinators, in turn, inform the physician and the physiotherapists responsible for the study.

1- Clinical Screening

The Medical Specialist in charge of the project will: (i) verify that the patients accomplish with the clinical and neuroimaging inclusion criteria in order to access the study; (ii) obtain the informed consent signed;

(iii) fill in the registration form and (iv) refer the patient to the neuropsychologist responsible for the project.

2- Neuropsychological screening with integrated cognitive evaluation

The neuropsychologist will perform a deep cognitive evaluation investigating: global cognitive functioning (Mini Mental State Examination) (29-30); presence of aphasia (Token Test, Aachener Aphasie Test, 33-34; oral naming, Batteria per l'Analisi dei Deficit Afasici, 35); spatial neglect (line and bell cancellation, 31-32; , 38; complex figure copy 39, 40; clock drawing test, 40; test for personal neglect, 41); ideomotor apraxia (movement imitation test, 36), and mood disorders (Hamilton Depression Rating Scale, 37). Patients will be randomly assigned to the MT or control group (CT).

Interventions

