- FIM (Functional Independent Measure): 18-voice scale that analyses different activities of daily life. The score in each item varies from 1 (complete dependence) to 7 (complete self-sufficiency), thus offering a cumulative score and a score profile in the various items. In this way the degree of self-sufficiency in performing elementary functional activities such as personal care, sphincter control, mobility, locomotion (motor area) and communication and social interaction (cognitive area) is measured. The administration of this scale will take about 10 minutes.

The primary outcome consists in the motor recovery of the upper limb, evaluated using the Fugl-Meyer scale (27). Secondary outcome are a specific physiatrist scale for the upper limb, the Action Research Arm Test (ARAT, 28), and a generic functional scale, the Functional Independent Measure (FIM, 26).

Sample size and randomization

Data analysis will be performed by a biostatistics, blind with respect to the treatments performed. The sample size will be constituted of 40 patients (randomized in 20 for the experimental group, MT, and 20 for the control group, CT).

Randomization will be performed according to the block randomization procedure, which allows to balance the quantitative asymmetry of the patients assigned to the two groups. The "block" is a sequence of the randomization list, which contains the same number of patients to be assigned to patients treated with MT and to controls (CT). For example, a block of 4 generates six different sequences, each of which assigns two patients to the MT group and two to the CT: MT-MT-CT-CT, MT-CT-MT-CT, CT-CT-MT, CT-MT-CT-MT, MT-CT-CT-MT, CT-MT-MT-CT. Thanks to the progressive balanced assignment, block randomization guarantees a similar number of patients enrolled in the two groups.

Statistical analysis

It was calculated to have a power of 0.80 and to demonstrate an effect size of .90 (difference between the two treatments equal to 90% of the variability of the phenomenon) to a Student t test for independent data, performed at a significance level of 0.05 (two-tailed test).

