Considering that the model of the analysis of covariance (ANCOVA), used for inferential analysis, has a greater expected efficiency (less residual variability) of at least 30%, it can be considered that the aforementioned sample size will allow to highlight also an effect size of around 0.7. The variables will be described by mean, median, standard deviation (quantitative variables) and absolute frequency and relative percentage (qualitative variables). Furthermore, for the differences between before and after treatment for the variables detected for each group, the 95% confidence intervals will be calculated. The analysis of the main and secondary variables will be carried out by analyzing the covariance (satisfied assumptions) with the base value as a covariate, the treatment group as a factor and inserting the variables relevant to the response to the treatment, which presented an unsatisfactory balance between the two groups at baseline. The effectiveness of the therapeutic intervention will be reported also in terms of effect size (difference between the variations of the scores in each group in relation to the total variance).

Expected results

The functional outcomes of stroke and the pathophysiological characteristics of the patients affected can be extremely variable. The standardization of patient groups is an extremely delicate moment in the design of efficacy studies of rehabilitation treatments. We believe that in this study a scrupulous standardization of the sample, the process of randomization, the separation of information between those responsible for patient assessment and data processing and analysis, may be the appropriate approach for the study of a correctly selected and homogeneous population.

Indeed, MT presents the scientific and physiological assumptions to positively impact on the patient's functional recovery with post-acute early-onset stroke. However, in order to highlight this aspect, it is necessary that the treatment is designed in strict relation with the patient's characteristics and that possible biases and interfering factors are carefully controlled.

Hopefully, with the careful execution of the proposed study design, it will be possible to demonstrate the efficacy of MT in the functional recovery process of the paretic upper limb of hemiplegic patients. This effective results will be expressed through the score improvement of the specific scales employed in the study.

Bibliography

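### Extra ANCOVA covariates enter on observed baseline imbalance, with no list, cut-off or lock; the primary model should be fixed before outcomes are seen

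*Combined protocol and SAP*

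**What the plan says.** The Statistical analysis section applies one ANCOVA rule to the primary outcome (Fugl-Meyer) and the secondary outcomes (ARAT, FIM). Baseline value and treatment group are always in the model. Further terms come in by "inserting the variables relevant to the response to the treatment, which presented an unsatisfactory balance between the two groups at baseline". No section lists the eligible variables, says how relevance or balance is judged, limits their number, or says that the choice is made before outcomes are seen.

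The pool of candidates is not small. Under neuropsychological screening, "The neuropsychologist will perform a deep cognitive evaluation investigating: global cognitive functioning" opens a list of five domains: global cognition, aphasia, neglect, apraxia and mood. Neglect alone has several tests, among them "complex figure copy 39, 40; clock drawing test, 40; test for personal neglect, 41", with no rule for combining them. Age and time since onset also appear, as eligibility limits ("Time post onset no longer than 4 weeks").

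Two other statements bear on the point, both about protection or efficiency. Under Sample size and randomization, "Data analysis will be performed by a biostatistics, blind with respect to the treatments performed". Under Statistical analysis, after assuming that ANCOVA is at least 30% more efficient, "it can be considered that the aforementioned sample size will allow to highlight also an effect size of around 0.7". Randomisation is in blocks that balance group numbers; no stratification factor is described.

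**The concern.** Two analysts who follow the text faithfully could fit different primary models to the same 40 patients. One might call a covariate unbalanced at p<0.05, another at a standardised difference above 0.25.

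Observed imbalance is also the wrong criterion in a randomised trial. A prognostic covariate reduces residual variance whether or not it is balanced. A non-prognostic covariate that happens to be imbalanced only widens the standard error of the treatment effect.

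What is at stake is the definition of the primary analysis. If the choice stays open until outcomes are available, the error rate of the reported test is no longer tied to the nominal 5%.

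**Working it through.** **1. The plan's own figures.** Inputs from Statistical analysis and Sample size: effect size 0.90, power 0.80, two-sided 0.05, 20 per arm.
- n per arm = 2(1.96 + 0.8416)² / 0.90² = 19.4, rounded up to 20, so 40 in total. This reproduces the plan; the exact noncentral t gives 79.2% power at 20 per arm.
- ANCOVA with 30% less residual variance: 0.90 × √0.70 = 0.753. If the 30% refers to the SD: 0.90 × 0.70 = 0.63. The stated value of around 0.7 lies between.

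These figures need only the baseline score, not the extra covariates.

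**2. How often a covariate is flagged by chance.** With 20 per arm, a standardised difference d gives t = d√10 on 38 degrees of freedom. For five independent candidates (one per screening domain, an assumption), the expected number flagged is 5p and the chance of at least one is 1 − (1 − p)⁵.

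| Cut-off | p for one | Expected of five | At least one of five |
|---|---|---|---|
| p<0.05 (d>0.64) | 5% | 0.25 | 23% |
| p<0.10 (d>0.53) | 10% | 0.5 | 41% |
| p<0.20 (d>0.41) | 20% | 1.0 | 67% |
| d>0.25 | 43% | 2.2 | 94% |
| d>0.2 | 53% | 2.7 | 98% |
| d>0.1 | 75% | 3.8 | over 99% |

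The unstated cut-off largely decides which model is fitted.

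**3. What an imbalanced, non-prognostic covariate costs.** Ignoring the baseline score, it multiplies the variance of the treatment estimate by 1 + t²/38 = 1 + 10d²/38. At d = 0.64 this is 1 + 4.10/38 = 1.108; at d = 0.25 it is 1 + 0.625/38 = 1.016. A strict cut-off admits few such terms but the costly ones; a loose one admits many.

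**4. Power by simulation.** Assumptions, none from the documents: 20 per arm in blocks of 4, baseline score explaining 30% of variance, true difference 0.75 SD, five independent candidates, and prognostic ones correlated r with what baseline leaves unexplained. Monte Carlo error is about 0.25 to 0.3 points. Power of the rule (%):

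| Candidates | p<0.05 | p<0.10 | p<0.20 | d>0.25 | d>0.2 | d>0.1 |
|---|---|---|---|---|---|---|
| None prognostic | 76.2 | 75.2 | 74.1 | 72.6 | 72.3 | 71.7 |
| Two at r=0.2 | 76.6 | 75.9 | 75.2 | 74.3 | 74.2 | 74.3 |
| Two at r=0.3 | 76.9 | 76.6 | 76.5 | 76.8 | 77.1 | 78.0 |

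Comparators:
- Baseline score only: 77.9%.
- One fixed non-prognostic covariate: 76.7%. Two: 75.4%.
- One fixed prognostic covariate: 78.3% at r=0.2 and 80.3% at r=0.3.

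The largest loss of the rule against baseline only is 77.9 − 71.7 = 6.2 points.

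If all five candidates are prognostic, the picture changes. At r=0.2 the rule gives 76.5 to 79.0% over the six cut-offs, against 77.7% with baseline only, 78.2% with one fixed covariate and 78.7% with two. At r=0.3 it gives 77.9 to 88.9%, against 80.4% with one fixed and 83.1% with two. The last case is optimistic, because the five jointly explain 5 × 0.3² = 45% of what baseline leaves.

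**5. Type I error by simulation.**
- One pre-set cut-off, two candidates: 4.8% at r=0, 4.4 to 4.7% at r=0.2, 3.9 to 4.4% at r=0.3, 3.3 to 4.0% at r=0.4. A fixed model gives 4.8%. With six candidates, all prognostic, it falls as low as 2.1%. The rule is conservative because an omitted covariate is nearly balanced: it adds little error to the estimate but still inflates the residual variance.
- Free choice of the most favourable result: 7.2 to 7.4% over baseline only and five cut-offs with six candidates; 7.2% (none prognostic) to 8.0% (two at r=0.3) over baseline only and six cut-offs with five candidates.

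**The case against.** The plan has two safeguards. Variables must be relevant to response as well as imbalanced, and the biostatistician is blind to treatment. If the relevance screen works, the non-prognostic scenarios above do not arise, and with loose cut-offs the rule can match or beat a model with one or two fixed covariates. Entry depends on baseline data, not outcomes. The error rate of 7 to 8% needs an analyst who compares models after seeing results, and nothing suggests that this is intended.

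Much of this stands. The power loss belongs to one scenario and is not a property of the rule. But relevance is undefined, so how well the screen works cannot be known or audited. Blinding restrains steering without defining the model: judging balance between groups needs at least coded allocation, and p-values can be compared across models under codes. No section locks the choice before outcomes.

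A reader might also infer that the rule inflates type I error by itself, or that it undermines the sample size and the assumed 30% efficiency. Neither is supported. A single pre-set cut-off is near nominal or conservative, and the sample-size argument rests on the baseline score, which is always in the model.

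**Conclusion.** The concern holds as a gap in prespecification, with a poor entry rule behind it. The primary and secondary models depend on the observed allocation and an unstated cut-off.

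The worst-case consequence is a type I error of about 7 to 8% under free choice; the blinded biostatistician limits this but does not exclude it. With any single pre-set cut-off it is about 3 to 5%, lower if many candidates are prognostic.

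A reader might conclude that the rule always costs power. It does not: it loses up to about 6 points against baseline only with five non-prognostic candidates, and gains when several are truly prognostic. The documents give no correlations, so all of these sizes are conditional on the assumptions listed. Nor do the documents support a particular number of extra covariates; a model with baseline score only also closes the gap.

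The change is worth making because it is cheap and settles the primary analysis, not because the present rule is shown to be invalid.

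**What to change.** Before any outcome data are seen, replace the imbalance clause with a fixed model for each outcome: T1 score on treatment group and baseline score. Use it either alone or with a short list of named baseline variables, already collected and expected to be prognostic, that are included whatever the observed balance. If spatial neglect is named, state the single test score or the classification rule. If days since onset is named, confirm that it is recorded as a value, since the protocol mentions it only as an eligibility limit, and note that its range is at most 4 weeks. Report any imbalance-driven model only as a sensitivity analysis.

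Cost: one sentence, and one residual degree of freedom of 37 (40 − 3) per named single-score variable. If the named variables prove non-prognostic, power against baseline only falls by 77.9 − 76.7 = 1.2 points for one and 77.9 − 75.4 = 2.5 points for two, so about 1 to 3 points. With baseline score only, that loss is nil. The other cost is a forgone gain if several unnamed candidates are strongly prognostic: with five at r=0.3 and the loosest cut-off, 88.9 − 83.1 = 5.8 points against two fixed covariates, and more against one or none. The sample size stays at 40.
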